## **Methods**

### *Participants*

Inclusion criteria: Adult ( $\geq 18$  years old) cancer patients who have completed primary cancer treatment (excluding long-term anti-hormone therapy, e.g., tamoxifen) at the Oncology Department at Aarhus University Hospital and who are experiencing moderate to severe pain measured as a score of  $\geq 4$  (0-10 NRS) on the following pain dimensions: a) pain intensity, b) pain burden, c) pain impact (function) and/or d) perceived need for help with pain management. Exclusion criteria:  $< 18$  years of age, not yet completed chemo or radiation therapy, metastases, and serious psychiatric diagnosis, e.g., psychosis. Patients seen by all four diagnosis teams at the Oncology Department at AUH are screened for pain (0-10 NRS) in connection with their final consultation with the oncologist. Patients with a pain score of  $\geq 4$  on one or more of the four pain dimensions questions receive a folder describing MBCT and the treatment plan and are encouraged to contact the MBCT team for more information and scheduling of an interview. If the patient, after initial information either by phone or after the first interview decline the offer to participate, but are willing to be contacted for the purpose of gathering more information about their reasons for not participating, we will send them a brief questionnaire concerning their pain and their reasons for choosing to decline the offer, to complete online. They are also asked to give their permission to collect the same information after three months. All data are collected and registered with REDCap [27], a high data security project administration system administered by Aarhus University's Clinical Trial Unit. Based on the 2014 pain audit results, we anticipate that of approx. 3,250 annually completed treatment plans across diagnoses, about 400 cancer patients will experience clinically significant pain (NRS score of  $\geq 4$  on one out of four pain dimensions) after completed primary treatment. From our experience with psychological treatment of cancer patients, we conservatively anticipate that approx. 35% will accept the offer and that 15% will drop out early, resulting in approx. 120 patients per year. It should be noted that the true extent of the need for psychological intervention for pain in the department is yet unknown. The present implementation project will help to determine this.

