### *Intervention*

As patients with significant pain are identified and accept the offer of receiving MBCT for pain, they will be consecutively included in groups of 12-20 participants. The patients will participate in eight weekly two hour

group sessions and will be asked to do an additional 45 minutes of daily training at home. The participants will be asked to record their home training to allow assessment of their adherence to the intervention. The program corresponds to the manualized MBCT program [28], but with adaptations that take into account the special needs of cancer patients [29, 30], including somewhat shorter sessions, shorter yoga exercises, and the omission of the all-day session. The sessions include psychoeducation and formalized mindfulness exercises with focus on the participants' here-and-now experience of their pain. According to the existing guidelines from Oxford Mindfulness Centre (OMC), Oxford University, where MBCT was developed, the instructor's professional and regular training, as well as supervision in MBCT, are critical for the quality of MBCT as intervention [31]. The instructors' training and supervision adhere to the OMC guidelines.

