### *Evaluation*

The aim of the present project is to evaluate the *practical implementation* of MBCT, with focus on: 1) the observed effects on pain (*primary outcome parameter*), 2) effects on quality-of-life (QoL) and on other cancer and cancer-treatment-related late effects associated with pain (*secondary outcome parameter*), 3) possible barriers for continued participation in the program (drop-out), 4) patient experience and satisfaction with the intervention and its organizational/practical implementation, 5) staff's experience of screening procedure and implementation, and 6) collection of data for use in the evaluation of effects, costs, and savings. For use in the evaluation, the patients complete questionnaires prior to the first session (T1), immediately after the last session (T2), and at a six-month follow-up (T3).

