### *Instruments*

The patient-reported measures at T1, T2, and T3 include:

- 1) T1-T3: Pain measures (pain intensity, pain burden, pain impact (function), and the need for help with pain management) (0-10 pt. NRS). The primary effect measure is pain intensity, which has been shown a valid measure of pain in cancer patients [32].
- 2) T1-T3: The patients' pain profile is assessed using a list of pain descriptors from the McGill Pain Questionnaire [33] and the *Douleur Neuropathique en 4 Questions* [Neuropathic Pain in Four Questions] [34]. The descriptors cover somatic, visceral, neuropathic and affective pain [35].
- 3) T1-T3: General QoL is measured using the EQ5D [36]. Other secondary outcomes include: depressive symptoms (Beck's Depression Index [37]), sleep difficulties (the Insomnia Severity Index [38]), cancer-related QoL (EORTC-QLQ-C30 [39, 40]), fear of cancer recurrence (FCRI-SF [41]), dispositional mindfulness (the Five Facet Mindfulness Questionnaire [42]), and self-compassion (the Self-Compassion Scales [43]).
- 4) T2-T3: Patient-experienced satisfaction with the treatment plan (5-pt. Likert Scale) and open questions concerning any experienced difficulties and challenges in connection with participation in the treatment plan.
- 5) For use in planned assessments of costs and savings, the participants are asked for their permission to collect relevant data from national and local registries. On the end of the project period, we will also explore the staff's impressions of the screening procedures and implementation with a brief questionnaire. Non-participants who have agreed to be contacted for further information will be contacted by email or phone and answer: 1) the four pain dimensions (at time points corresponding to T1-T3) and 2) a questionnaire with closed and open questions concerning their reasons for not participating, e.g., time, geography, attitude

towards psychological pain intervention (barriers) and what help, if any, they receive to manage their pain, e.g., pain medication, physiotherapy, psychological help, own activities (resources) (T1).

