### *Statistical analysis*

Intention-to-treat (ITT) analyses will be conducted with Multilevel Linear Models (MLMs). In the analysis, we will focus on 1) changes over time (T1-T3) in pain measurements. We will also compare patients who experience statistically (Reliable Change Index) [44] and clinically significant changes (NRS  $\geq 2$ ) [45] with the remaining patients. In the secondary analyses, we will focus on 1) effects on QoL and other secondary outcomes and explore the possible moderating influence of demographic and clinical background variables to changes in pain. Additionally, we will investigate 3) the staff's impressions of screening procedures and implementation. Furthermore, 4) nonparticipants will be studied with regard to changes in pain and reasons for not participating (barriers and resources). 5) If the implementation is deemed successful, cost analyses will be conducted on the basis of outcomes and registry data concerning health care utilization.

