### **Dissemination**

The results will be sought published in a report focusing on: 1) the effects of the implemented program on pain, 2) the effects on QoL and other secondary outcomes associated with pain, e.g., depressive symptoms, sleep disturbance, 3) the reasons for patient nonparticipation, 4) patient satisfaction with the treatment program, and 5) the staff's experience of screening procedures and implementation. Furthermore, if successful, a further report will be produced, focusing on 6) costs and possible savings obtained by implementing the intervention as standard treatment for post-treatment pain in the department.

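### Costs are analysed and reported only if the implementation is judged a success, which the plan does not define, and the result is called savings although no cost comparator is specified

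*Combined protocol and SAP*

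**What the plan says.** All sections cited are in the combined protocol and SAP.

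- **Evaluation** lists as its sixth focus "collection of data for use in the evaluation of effects, costs, and savings". No condition is attached.
- **Instruments** adds: "For use in planned assessments of costs and savings, the participants are asked for their permission" to obtain data from national and local registries. Again there is no condition.
- **Statistical analysis** sets one: "If the implementation is deemed successful, cost analyses will be conducted on the basis of outcomes and registry data concerning health care utilization".
- **Dissemination** names five topics for the main report without any condition. It then continues: "Furthermore, if successful, a further report will be produced", whose subject is "costs and possible savings obtained by implementing the intervention as standard treatment".
- **Participants** places the pain screening "in connection with their final consultation with the oncologist".
- **Intervention** says of patients who accept the offer that "they will be consecutively included in groups of 12-20 participants". No control arm is described anywhere.
- **Perspectives** expects implementation to be at least cost-neutral, on the basis of savings seen in the earlier randomised trial.

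**The concern.** Two things are at stake.

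The first is selective reporting. Costs are the only result that depends on a favourable judgement of the implementation, and the plan leaves that judgement open. A department deciding whether to adopt MBCT would learn what it cost only where the implementation had already been called a success. The expectation of cost-neutrality would go unchecked in the situation where it is most in doubt.

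The second is attribution. The wording in Dissemination ties savings to the intervention. Without a comparator, a fall in health care use that would have happened anyway could be read as a saving produced by MBCT.

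**Working it through.** **1. The plan's own cost figures.** Perspectives gives DKK 5,421 saved per patient over eight months.

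- Annualised: 5,421 × 12 / 8 = 8,131.5 (stated: DKK 8,131).
- For 120 patients: 8,131.5 × 120 = 975,780 (stated: about DKK 975,780).
- Intake (Participants): 400 × 0.35 × 0.85 = 119 (stated: approx. 120).

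The figures reproduce. The savings come from the earlier randomised trial, so the absence of a comparator in this trial does not touch them.

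**2. Which results are conditional.** Dissemination, item by item:

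| Topic | Condition on reporting |
|---|---|
| Effects on pain | none |
| Quality of life and other secondary outcomes | none |
| Reasons for nonparticipation | none |
| Patient satisfaction | none |
| Staff experience | none |
| Costs and possible savings | only if successful |

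Statistical analysis places the same condition on doing the cost analysis at all.

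**3. Whether success is defined.** No section sets a threshold for the implementation in terms of pain change, uptake, drop-out, satisfaction or staff opinion. The change of 2 points or more on the pain scale in Statistical analysis classifies individual patients and is not linked to success of the implementation. No decision-maker or decision date is given. Nothing requires the judgement to be made before outcomes or registry data are seen.

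**4. What cost contrast the data allow.**

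- Patients who accept all enter MBCT groups, so no concurrent untreated group is formed by design.
- Registry permission is described for participants. Consenting non-participants give pain scores, reasons for declining and the help they receive; no registry data are described for them.
- No registry window, reference period or costing method is stated.

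That leaves participants' own use before and after MBCT. This follows from the data described; the plan does not state it.

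**5. Why before-after would be hard to read.** Screening takes place at the last oncology consultation, so a period before MBCT may include primary treatment. Use may then fall for reasons unrelated to MBCT. The documents give no figure for such a change, so no bias estimate is attempted.

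**The case against.** The strongest reply is that this is sensible sequencing: obtain permission at the start, and spend effort on a health-economic report only if the programme proves viable. That is largely right about coherence. A reader might infer that Evaluation and Instruments contradict Statistical analysis, but the documents do not support that. The former concern gathering data and permission, the latter whether to analyse them, and a planned analysis can be conditional.

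It is also fair that the condition is on success of the implementation and not on a favourable cost result. A reader might infer that the plan selects directly on the cost finding; the text does not say so. A disappointing implementation would still be visible through the five unconditional topics. What remains is that its costs would not be.

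On savings, a reader might infer that the plan commits to presenting an uncontrolled before-after change as an effect of MBCT. No section states such an analysis. The wording is hedged, and it could describe a departmental projection like the one in Perspectives. What stands is narrower: savings are to be reported as obtained through the intervention, and no comparator is specified that would support that attribution.

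**Conclusion.** The point holds as one of selective reporting, together with a savings claim that lacks a stated comparator. The first part is plain from the text. The second rests on two assumptions: that the registry data will be those described, from participants only, and that no comparator is planned elsewhere.

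The size and direction of any bias in reported savings cannot be derived from the documents. Nor do they show that health care use would in fact fall without MBCT, only that the timing of screening makes this possible.

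Severity is minor. The primary outcome, pain intensity, is untouched, and costs are not among the four objectives. It is still worth correcting, because the change is small and the cost report is meant to inform use of MBCT as standard treatment.

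**What to change.** 1. In Statistical analysis and in Dissemination, delete the success condition. Possible wording: *Cost analyses will be carried out and reported whatever the pain or implementation results.*
2. Describe the cost of MBCT and participants' health care use as descriptive results, not as savings caused by MBCT, unless a comparator is specified.
3. If the condition is kept for resource reasons, the weaker alternative is to fix the success criterion and the decision date before any registry data are seen, and to state in the main report if the cost analysis was not done and why.

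The edit itself is a few words in two sections. The commitment behind it is some analysis work, possibly a registry extraction that would otherwise not be made, and a cost message that may be less favourable.

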### **Dissemination**

The results will be sought published in a report focusing on: 1) the effects of the implemented program on pain, 2) the effects on QoL and other secondary outcomes associated with pain, e.g., depressive symptoms, sleep disturbance, 3) the reasons for patient nonparticipation, 4) patient satisfaction with the treatment program, and 5) the staff's experience of screening procedures and implementation. Furthermore, if successful, a further report will be produced, focusing on 6) costs and possible savings obtained by implementing the intervention as standard treatment for post-treatment pain in the department.

### **Perspectives**

Persistent pain is a late effect of cancer and cancer treatment that constitutes a significant problem for the individual patient, health services and society [2, 46]. Consequently, the need exists for available evidence-based treatments for such problems to be implemented in health services [25, 47]. The project is in line with Aarhus University Hospital's desire to develop and implement evidence-based strategies for the prevention and treatment of late effects of cancer and cancer treatment. The analysis of health-economic data from our published RCT [26] showed an average savings in health services consumption (including MBCT expenses) per patient having completed therapy of approx. DKK 5,421 over an eight-month period. When this data is extrapolated to correspond to one year, savings of DKK 8,131 per participant are achieved, giving net savings for total consumption of health services of about DKK 975,780 per year for 120 patients. As such, the implementation of MBCT as a treatment program for post-treatment pain in cancer patients is expected to be cost-neutral, at minimum, while *at the same time*, expecting a clinically significant reduction in pain among those patients who accept the treatment plan.

### **Ethics**

We will adhere to the rules and guidelines as formulated by the Helsinki Declaration-II and the Danish Data Protection Agency. Withdrawal from the project or otherwise will have no influence on the patients treatment. The Regional Ethical Committee has evaluated the project as a questionnaire survey which does not involve human biological material and therefore does not need approval from the Committees, Act number 1083 of 15th September 2017, section § 14 (2) (appendix 1).

